#### 3.5 END OF TREATMENT ASSESSMENTS

The participant will continue on study drug until there is evidence of tumor progression, intolerable toxicities, completion of 12 cycles, or withdraws from treatment (refer to Section 3.9.1). The "End of Treatment" assessments (Section 3.7) will be performed 7-35 days after completing the last dose of study drug or before the initiation of a new anti-cancer treatment, whichever comes first. If the participant cannot return to the study center for this visit, the participant may complete assessments locally, including seeing a local physician for a physical exam and local clinical laboratories, and the study team will follow-up with the participant remotely. Imaging scans need only be performed at end of treatment, if not performed within the last 4 weeks.

#### 3.6 FOLLOW-UP PERIOD

## 3.6.1 30-day Follow-up Visit

The mandatory Safety Follow- up visit should be conducted approximately 30 (+ 5 days) after the last dose of study drug and before initiation of a new anti-cancer treatment, whichever comes first (see assessments, Section 3.7). In addition, the study team will confirm contact information for participant and a designated family member, and remind participant of follow-up contact that will be conducted for survival status.

## 3.6.2 Survival Follow-up

Overall survival will be collected until 1 year post-last dose of Minnelide. Participants will be contacted remotely (e.g., phone or email) approximately every 90 days. If participants are still being seen at the NIH, this information may be obtained from the medical records.

Version Date: 7/10/2025

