#### 3 STUDY IMPLEMENTATION

#### 3.1 STUDY DESIGN

This is a Phase II single arm, single cohort study that will enroll up to 25 evaluable participants with advanced ASCP that has been previously treated. In order to account for screen failures and inevaluable patients (i.e., participants who are not evaluable for the primary endpoint of response), the accrual ceiling will be set at 55 participants.

Accrual may continue up to 15 treated participants while the primary objective is being determined but no new participants may be accrued once it is known that this criteria has not been met (see Sections 10.3 and 10.5.6).

Initial participants will self-administer Minnelide at 2 mg PO daily on Days 1-21 of each 28 days cycle. Those joining the study after modification dated 3/10/23 will receive Minnelide at 2.5 mg PO daily on Days 1-21 of each 28 days cycle. Participants initially enrolled at the 2 mg dose may be increased to the 2.5 mg dose at the discretion of the study team if they have been tolerating the lower dose (i.e., intrapatient dose escalation is permitted). Treatment will continue for up to 12 cycles (1 year) in the absence of disease progression or unacceptable toxicity. After initiation of treatment, restaging scans will be conducted approximately every 2 cycles or 8 weeks. Optional biopsies will be requested mid-cycle 1 and at time of progression.

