## 6.3.3.3 Evaluation of Best Overall Response

The best overall response is the best response recorded from the start of the treatment until disease progression/recurrence (taking as reference for progressive disease the smallest measurements recorded since the treatment started). The participant's best response assignment will depend on the achievement of both measurement and confirmation criteria.

For Participants with Measurable Disease (i.e., Target Disease)

Target Lesions	Non-Target Lesions	New Lesions	Overall Response	Best Overall Response when Confirmation is Required*
CR	CR	No	CR	≥4 wks. Confirmation**
CR	Non- CR/Non-PD	No	PR	
CR	Not evaluated	No	PR	≥4 wks. Confirmation**
PR	Non- CR/Non- PD/not evaluated	No	PR	
SD	Non- CR/Non- PD/not evaluated	No	SD	Documented at least once ≥4 wks. from baseline**
PD	Any	Yes or No	PD	
Any	PD***	Yes or No	PD	no prior SD, PR or CR
Any	Any	Yes	PD	

Version Date: 7/10/2025

Target	Non-Target	New	Overall	Best Overall Response when
Lesions	Lesions	Lesions	Response	Confirmation is Required*

- \* See RECIST 1.1 manuscript for further details on what is evidence of a new lesion.
- \*\* Only for non-randomized trials with response as primary endpoint.
- \*\*\* In exceptional circumstances, unequivocal progression in non-target lesions may be accepted as disease progression.

Note: Participants with a global deterioration of health status requiring discontinuation of treatment without objective evidence of disease progression at that time should be reported as "symptomatic deterioration." Every effort should be made to document the objective progression even after discontinuation of treatment.

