### 6.3.4 Progression-Free Survival

PFS is defined as the duration of time from start of treatment to time of progression or death, whichever occurs first.

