## 10 STATISTICAL CONSIDERATIONS

### 10.1 OBJECTIVES AND ENDPOINTS

OBJECTIVES	ENDPOINTS	JUSTIFICATION FOR ENDPOINTS
Primary		
To determine the single agent antitumor activity (disease control rate) of the anti-superenhancer agent Minnelide in participants with advanced, previously treated ASCP	Assess disease control rate in the study population, where disease control = best response of CR, PR or at least 16 weeks of stable disease	Establishing disease control in 8 or more of 25 participants with advanced previously treated ASCP would be considered clinically significant.
Secondary		
Determine Minnelide safety in participants with advanced, previously treated ASCP	Identify Adverse Events of grade 2 and above (per CTCAE criteria, version 5.0) related to Minnelide that occur from start of treatment to 30 days after last treatment.	Descriptive endpoint to assess toxicity profile of the study drug in this population.
	Assess rate of Serious Adverse Events related to Minnelide that occur from start of treatment to 30 days after last treatment.	
Assess alternative measures of anti- tumor activity	Determine median time until disease progression, switch to a new systemic treatment or death in the treated population. Data cut-off will occur 1 year after last Minnelide treatment.	Descriptive endpoints that may help to determine sample size needed for future Phase 3 study
	Determine median time until death in the treated population. Data cut-off will occur 1 year after last Minnelide treatment.	
	Determine objective response rate of Minnelide.	

OBJECTIVES	ENDPOINTS	JUSTIFICATION FOR ENDPOINTS
Exploratory		
Identify factors that influence participant response to treatment through detailed molecular analysis of participant tumor, serum and blood cell samples acquired at baseline, on-treatment and at time of progression	For each patient with available samples, we will describe the following properties and consider associations with patient response to therapy:	These endpoints have been selected to help understand why the drug may or may not work, to allow better design of future studies in this patient population.
	Tumor genetic mutations at baseline and at time of progression	Do specific genetic profiles give a patient higher or lower likelihood or response? Does treatment change mutational profile?
	Treatment-related change (between pre-treatment baseline and ~C1D15) in:	

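### After treatment stops without progression, the plan schedules one conditional scan and then survival contacts only, which does not supply the dates that PFS and 16-week stable disease need

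*Combined protocol and SAP*

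**What the plan says.** **Endpoints.** Section 10.1 sets the primary endpoint as "disease control = best response of CR, PR or at least 16 weeks of stable disease". A secondary endpoint is "Determine median time until disease progression, switch to a new systemic treatment or death in the treated population", and "Data cut-off will occur 1 year after last Minnelide treatment". Section 6.3.4 defines PFS differently: "PFS is defined as the duration of time from start of treatment to time of progression or death, whichever occurs first". New treatment is not an event there.

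**Imaging on treatment.** Section 3.1: "After initiation of treatment, restaging scans will be conducted approximately every 2 cycles or 8 weeks". Section 3.4 and the section 3.7 calendar also tie scans to cycles.

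**Imaging after treatment.** The end-of-treatment visit falls 7 to 35 days after the last dose, or before new anti-cancer treatment if that is sooner. Section 3.5 adds: "Imaging scans need only be performed at end of treatment, if not performed within the last 4 weeks". The calendar has no imaging entry in the 30-day or survival columns.

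**Later contacts.** Section 3.6.2: "Overall survival will be collected until 1 year post-last dose of Minnelide", by remote contact about every 90 days or from NIH records.

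**Other text that bears on this.** Section 6.3 asks for response re-evaluation at 8-week intervals and does not confine this to time on treatment. Section 6.3.3.3 says "Every effort should be made to document the objective progression even after discontinuation of treatment", but only about symptomatic deterioration. Section 3.9.1 takes participants off therapy for several reasons other than progression. Under section 3.9.2, stopping therapy does not take a participant off study.

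**The concern.** Participants who stop for toxicity, intercurrent illness, their own request or completion of 12 cycles stay in follow-up, but the plan stops asking for two of the three event types in the section 10.1 endpoint.

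For PFS this has two possible results. Censoring at the last scan is likely to be informative, because people who stop early may differ in risk from those still being scanned. If only deaths are counted after the last scan, a later death stands in for an earlier progression and PFS is too long.

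For the primary endpoint, a participant who is stable at week 8 and stops soon afterwards is evaluable under section 10.4.2, having had at least one cycle and a repeat assessment. That participant is therefore in the denominator. Nothing says whether they count as disease control when no scan reaches week 16.

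**Working it through.** **1. The plan's own design figure.** Inputs from section 10.3: p0 = 0.20, p1 = 0.40, stop at 0–2 of 12, positive at 8 or more of 25. The probability of early termination under p0 is the sum over x = 0, 1, 2 of C(12,x)·0.2^x·0.8^(12−x) = 0.0687 + 0.2062 + 0.2835 = 0.558. This matches the stated 55.8%. The exact two-stage type I error is 0.099 and the power 0.815. A full search returns the same design as Simon-optimal. The design is sound, and the question is what data feed it.

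**2. Can the end-of-treatment scan reach week 16?** Week 16 is day 112. With last dose on day L, the visit window is L + 7 to L + 35 (section 3.5), assuming no cycle delay and no earlier start of new treatment.

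| Last dose | Study day L | Visit window (days) |
|---|---|---|
| Cycle 1, day 21 | 21 | 28–56 |
| Cycle 2, day 21 | 49 | 56–84 |
| Cycle 3, day 21 | 77 | 84–112 |
| Cycle 4, day 21 | 105 | 112–140 |

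The latest visit reaches day 112 only if L ≥ 112 − 35 = 77. The earliest does so only if L ≥ 112 − 7 = 105. Before day 77 the scan cannot reach week 16. From day 77 to day 104 it depends on when the visit falls. From day 105 it always does.

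**3. An example.** A participant is stable on the week-8 scan (about day 56) and takes the last dose on day 70. The window is days 77–105. Counting the 4 weeks back from the visit, the week-8 scan lapses at day 56 + 28 = 84, so a scan is required for most of the window. It could show progression and so refute stable disease. It cannot confirm stability at day 112.

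**4. The PFS gap after 12 cycles.** Last dose: 28 × 11 + 21 = day 329. Latest end-of-treatment visit: 329 + 35 = day 364. Cut-off: 329 + 365 = day 694. That leaves 694 − 364 = 330 days with no scheduled imaging, room for five 8-week scans (330/56 = 5.9).

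**5. How many participants?** Section 1.2.2.2.2 reports 6 of 67 in the oral phase 1 study stopping for a treatment-emergent event. Four of the six were grade 5 (two sepsis, two disease progression). Those are deaths, which later imaging could not have helped. The non-fatal stops are 2/67 = 3.0%, and 0.030 × 25 is about 0.7 participants. The 67 include 24 on combination therapy. The rate at this trial's doses, and the rate of other early stops, are not given.

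**6. What the unstated rule could do.** These are assumed fractions, not figures from the documents.

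- If a fraction f of truly controlled participants lacks a week-16 scan and counts as failures, the observed rate is 0.40(1 − f). Power is 0.759 at f = 5%, 0.694 at 10% and 0.540 at 20%.
- If a fraction g of true failures counts as controlled because nothing contradicts it, the observed null rate is 0.20 + 0.80g. Type I error is 0.140 at g = 2% and 0.216 at g = 5%.

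One participant is 1/25 = 4 percentage points: 8/25 = 32% is positive and 7/25 = 28% is not.

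**The case against.** The best defence has four parts.

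- **The data are not absent.** One scan is scheduled after the last dose, deaths are collected for a year, and the 30-day visit records concomitant medication, which could catch an early switch of treatment. All of this stands. A reader might infer that no imaging follows discontinuation, or that PFS cannot be determined, but the documents do not support either. Kaplan-Meier estimation can proceed. What is missing is later progression and new-treatment dates and a censoring rule.
- **The median may hardly move.** Section 12.3.3 expects median survival of no more than 3 months, and the PFS output is descriptive. Gaps after 12 cycles are therefore unlikely to shift it. This stands for late gaps, less so for early stops.
- **On-treatment disease control is a legitimate design choice.** Requiring documented stability naturally makes undocumented cases non-successes. That is the conservative reading, but the plan does not state it.
- **Section 6.3 already asks for 8-weekly re-evaluation.** Its wording is not limited to treatment, but sections 3.1 and 3.4 and the calendar tie scans to cycles. The text is inconsistent and does not settle the matter.

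A reader might also scale 6 of 67 to about 2 of 25 (0.0896 × 25 = 2.2). The four fatal events in that count rule this out as a measure of the problem.

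**Conclusion.** The concern holds in a limited form. Apart from one conditional scan, nothing scheduled after the 30-day visit collects progression or new systemic treatment, although section 10.1 needs both up to 1 year after the last dose. PFS is therefore open to informative censoring or to death replacing progression.

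The primary endpoint is affected only for participants with stable disease and no CR or PR who stop too early for a week-16 scan: certainly with a last dose before about day 77, and possibly up to day 104. Those with CR or PR, those scanned at or after week 16, and 12-cycle completers are unaffected for the primary endpoint.

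The number affected is unknown. From non-fatal adverse-event stops alone it is about 0.7 of 25, assuming the phase 1 rate carries over and all such stops are early. Other reasons for stopping add an amount that the documents do not quantify. The effect is probably small, but it matters because one participant separates a positive from a negative result. The power and type I error figures show sensitivity to assumed fractions and are not forecasts.

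The documents do not support going further and requiring new 8-weekly scans after treatment. That is an additional procedure, and it is not needed to close the data gap.

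**What to change.** 1. **Sections 3.6.2 and 3.7.** Have the existing 90-day contacts and record reviews also collect (a) date and basis of progression, from scans already done locally or at NIH, and (b) start date and type of any new systemic treatment.
2. **Section 10.5.2.** State that stable disease not documented by a scan at or after week 16 counts as not achieved, with the participant kept in the denominator. Name a window so that the scheduled scan before cycle 5 qualifies. Cycle 5 day 1 is day 4 × 28 + 1 = 113, and section 3.4 allows the scan up to 3 days before, that is from day 110.
3. **Section 10.5.3.** State that PFS is censored at the last adequate scan when no event is documented.
4. **Reconcile the text.** Section 6.3 should agree with sections 3.1, 3.4 and 3.7 on whether 8-weekly re-evaluation continues after treatment. Section 6.3.4 should agree with section 10.1 on whether new systemic treatment is a PFS event.

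The cost is two data items per planned contact and a small amendment. The counting rule may slightly lower the disease control rate, and it does not recover power lost to missing scans. Using scans already done reduces that loss. Sample size and decision limits stay as they are.

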## 3.7 STUDY CALENDAR

Procedure	Screening	Cycle 1				Subsequent Cycles		End of	Follow-up		
		Base Da		Day 8	Day 15	Day 22	Day 1	Day 15	treatment visit	30-day Follow-up	Survival Follow-up
Window(s):	Section 2.3.2	≤7 days	≤3 days	±2 days	±2 days	±2 days	≤3 days	±2 days	Section 3.5	Section 3.6.1	Section 3.6.2
Informed Consent	X										
Confirmation of diagnosis	X										
Medical History	X										
Symptom Assessment	X		X	X	X	X	X	X			
Physical Exam	X	X			X		X		X		
Vital Signs	X	X			X		X		X		
Height	X										
Weight	X	X					X				
Performance Status (ECOG)	X	X			X		X		X		
Clinical laboratories											
CBC with differential	X		X	X	X	X	X	X	X		
Serum chemistries	X		X	X	X	X	X	X	X		
PT/INR and aPTT	X										
Urinalysis	X		X				X		X		
HBsAg and HCV RNA	X										
Pregnancy Test (serum)	X		X				X		X	X	
Serum Tumor Markers			X				X		X		
ECG	X								X		
Imaging scans (CT/MRI)	X						X (every other cycle)		X		
Adverse Events		X		X	X	X	X	X	X	X	
Concomitant Medications	X	X			X		X		X	X	
Review Participant Dosing Diary and Drug Accountability			X		X		X				
Dispense Minnelide			X				X				

Version Date: 7/10/2025

Procedure	Screening	Cycle 1				Subsequent Cycles			Follow-up		
		Basel Day		Day 8	Day 15	Day 22	Day 1	Day 15	treatment visit	30-day Follow-up	Survival Follow-up
Minnelide administration					y 7 day		sing for 21 d week 4 of 6				
Review Contraception		X			X		X		X	X	
Review Contact Information									X	X	
Correlative research	See	Section 5.2 for windows for Correlative Research samples.									
Blood Sample(s)		X			X		X (C2D1 only)		X (or PD)		
Tumor Biopsy (optional)		X			X				X (or PD)		
Archival Tissue	X	X									
NIH Advance Directives Form		X									
Survival		X X				X					

**NOTE:** Other tests/assessments should be completed as clinically indicated. For a description of all on study assessments, see Section **3.4**.

Version Date: 7/10/2025

#### 3.8 COST AND COMPENSATION

#### 3.8.1 Costs

NIH does not bill health insurance companies or participants for any research or related clinical care that participants receive at the NIH Clinical Center. If some tests and procedures are performed outside the NIH Clinical Center, participants may have to pay for these costs if they are not covered by an insurance company. Medicines that are not part of the study treatment will not be provided or paid for by the NIH Clinical Center.

## 3.8.2 Compensation

Participants will not be compensated on this study.

#### 3.8.3 Reimbursement

The NCI will cover the costs of some expenses associated with protocol participation. Some of these costs may be paid directly by the NIH and some may be reimbursed to the participant/guardian as appropriate. The amount and form of these payments are determined by the NCI Travel and Lodging Reimbursement Policy.

No reimbursement is provided to participants enrolled at sites other than NIH Clinical Center.

#### 3.9 CRITERIA FOR REMOVAL FROM PROTOCOL THERAPY AND OFF STUDY CRITERIA

Prior to removal from study, effort must be made to have all participants complete a safety visit (See Study Calendar).

## 3.9.1 Criteria for removal from protocol therapy

A participant must be discontinued from the protocol therapy for any of the following reasons:

- Completed 12 cycles of trial treatment
- Confirmed disease progression
- Participants request to be withdrawn from active therapy
- Unacceptable adverse experiences as described in Section 3.3
- Inter-current illness that prevents further administration of treatment
- Investigator Discretion
- The participant has a confirmed positive serum pregnancy test
- Noncompliance with trial treatment or procedure requirements

## 3.9.2 Off-Study Criteria

A participant who meets one of the following criteria will be considered Off Study:

- Participant requests to be withdrawn from study
- Death
- Screen failure

#### 3.9.3 Lost to Follow-up

A participant will be considered lost to follow-up if he or she fails to return for three scheduled visits and is unable to be contacted by the study site staff.

The following actions must be taken if a participant fails to return to the clinic for a required study visit:

Version Date: 7/10/2025

• The site will attempt to contact the participant and reschedule the missed visit within three business days and counsel the participant on the importance of maintaining the assigned visit schedule and ascertain if the participant wishes to and/or should continue in the study.

- Before a participant is deemed lost to follow-up, the investigator or designee will make
  every effort to regain contact with the participant (where possible, 3 telephone calls and, if
  necessary, an IRB-approved certified letter to the participant's last known mailing address
  or local equivalent methods). These contact attempts should be documented in the
  participant's medical record or study file.
- Should the participant continue to be unreachable, he or she will be considered to have withdrawn from the study with a primary reason of lost to follow-up.

## 4 CONCOMITANT MEDICATIONS/MEASURES

Necessary supportive measures for optimal medical care may be given throughout the study, including IV antibiotics to treat infections, blood components, and antiemetics. Additional care will be administered as indicated by the treating physician and the participant's medical need.

No concomitant cytotoxic therapy, whether conventional or investigational, will be allowed during this study. All concomitant medications and supportive therapy must be recorded on the appropriate CRF.

Palliative radiotherapy may be permitted at the discretion of the PI while the participant is undergoing treatment.

All concomitant medications received within 30 days before the first dose of trial treatment and at the 30 day (+ 5 days) follow-up visit should be recorded.

In vitro studies suggest that Minnelide has a low potential for CYP450 related drug-drug interactions.

Minnelide is a substrate for but not an inhibitor of P-glycoprotein. Co-administration with inhibitors of glycoprotein is permitted with caution.

Ondansetron may not be given with Minnelide. It was noted in the Phase 1 study that participants receiving ondansetron in conjunction with Minnelide had higher serum Minnelide concentrations. Follow-up of this observation in murine models confirmed that co-administration of ondansetron with Minnelide increased Minnelide exposures. The mechanism for this interaction is unknown. Other 5-HT3 receptor antagonists did not produce this interaction and are acceptable.

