#### 1 INTRODUCTION

#### 1.1 STUDY OBJECTIVES

## 1.1.1 Primary Objective

 To determine the single agent antitumor activity (disease control rate) of the antisuperenhancer agent Minnelide in participants with advanced, previously treated ASCP

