#### **6.3.1** Disease Parameters

Measurable disease: Measurable lesions are defined as those that can be accurately measured in at least one dimension (longest diameter to be recorded) as:

- By chest x-ray:  $\geq$ 20 mm;
- By CT scan:
  - O Scan slice thickness 5 mm or under: as >10 mm
  - O Scan slice thickness > 5 mm: double the slice thickness
- With calipers on clinical exam: >10 mm.

All tumor measurements must be recorded in millimeters (or decimal fractions of centimeters).

Note: Tumor lesions that are situated in a previously irradiated area might or might not be considered measurable. If the investigator thinks it appropriate to include them, the conditions under which such lesions should be considered must be defined in the protocol.

Malignant lymph nodes. To be considered pathologically enlarged and measurable, a lymph node must be  $\geq 15$  mm in short axis when assessed by CT scan (CT scan slice thickness recommended to be no greater than 5 mm). At baseline and in follow-up, only the short axis will be measured and followed.

Non-measurable disease. All other lesions (or sites of disease), including small lesions (longest diameter <10 mm or pathological lymph nodes with  $\ge10$  to <15 mm short axis), are considered non-measurable disease. Bone lesions, leptomeningeal disease, ascites, pleural/pericardial

Version Date: 7/10/2025

effusions, lymphangitis cutis/pulmonitis, inflammatory breast disease, and abdominal masses (not followed by CT or MRI), are considered as non-measurable.

Note: Cystic lesions that meet the criteria for radiographically defined simple cysts should not be considered as malignant lesions (neither measurable nor non-measurable) since they are, by definition, simple cysts.

'Cystic lesions' thought to represent cystic metastases can be considered as measurable lesions, if they meet the definition of measurability described above. However, if non-cystic lesions are present in the same participant, these are preferred for selection as target lesions.

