## 6.3.3 Response Criteria

## 6.3.3.1 Evaluation of Target Lesions

Complete Response (CR): Disappearance of all target lesions. Any pathological lymph nodes (whether target or non-target) must have reduction in short axis to <10 mm.

Partial Response (PR): At least a 30% decrease in the sum of the diameters of target lesions, taking as reference the baseline sum of diameters.

Progressive Disease (PD): At least a 20% increase in the sum of the diameters of target lesions, taking as reference the smallest sum on study (this includes the baseline sum if that is the smallest on study). In addition to the relative increase of 20%, the sum must also demonstrate an absolute increase of at least 5 mm. (Note: the appearance of one or more new lesions is also considered progressions).

Stable Disease (SD): Neither sufficient shrinkage to qualify for PR nor sufficient increase to qualify for PD, taking as reference the smallest sum of diameters while on study.

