# 6.3.3.2 Evaluation of Non-Target Lesions

Complete Response (CR): Disappearance of all non-target lesions and normalization of tumor marker level. All lymph nodes must be non-pathological in size (<10 mm short axis).

Note: If tumor markers are initially above the upper normal limit, they must normalize for a participant to be considered in complete clinical response.

Non-CR/Non-PD: Persistence of one or more non-target lesion(s) and/or maintenance of tumor marker level above the normal limits.

Progressive Disease (PD): Appearance of one or more new lesions and/or unequivocal progression

Version Date: 7/10/2025

of existing non-target lesions. *Unequivocal progression* should not normally trump target lesion status. It must be representative of overall disease status change, not a single lesion increase.

Although a clear progression of "non-target" lesions only is exceptional, the opinion of the treating physician should prevail in such circumstances, and the progression status should be confirmed at a later time by the review panel (or Principal Investigator).

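### Palliative radiotherapy is allowed on treatment with no counting rule, so a radiation effect on a target lesion can be scored as disease control in a single-agent endpoint

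*Combined protocol and SAP*

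**What the plan says.** Section 4 excludes concomitant cytotoxic therapy but then says: "Palliative radiotherapy may be permitted at the discretion of the PI while the participant is undergoing treatment". It gives no restriction on site, timing, or whether the lesion is a target lesion.

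Section 1.1.1 sets the primary objective as single-agent antitumour activity. Section 10.1 defines the endpoint: "disease control = best response of CR, PR or at least 16 weeks of stable disease". The parts of Section 6.3 that feed it are:

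- Section 6.3.1 takes up to five measurable lesions as targets, at most two per organ, and sums their diameters.
- Section 6.3.3.1 defines PR as "At least a 30% decrease in the sum of the diameters of target lesions" relative to baseline, and SD by the same sum.
- Section 6.3.3.2 includes in PD "Appearance of one or more new lesions and/or unequivocal progression" of existing non-target lesions.
- Section 6.3.3.3 states: "The best overall response is the best response recorded from the start of the treatment until disease progression/recurrence". Its table requires confirmation of CR and PR at four weeks or more.

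Sections 10.4 and 10.5 contain no rule for radiotherapy given on study. It does not make a lesion non-evaluable, it does not count as a failure, and no sensitivity analysis addresses it.

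**The concern.** With no control arm, the count of participants with disease control is the whole of the evidence. If some of those counts come from local radiation, the rate no longer measures what Minnelide does alone.

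Elsewhere the plan treats radiotherapy as capable of affecting the tumour. Exclusion 2.1.2.4 requires two weeks between prior radiotherapy and Cycle 1 Day 1, alongside chemotherapy and targeted agents. The secondary time-to-event endpoint in Section 10.1 counts a switch to new systemic treatment as an event, but local therapy given on study has no counterpart in any endpoint.

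The situation is plausible. Locally advanced unresectable disease is eligible (Précis), so a single site may dominate the target sum, and Section 12.3.2 names pain as a tumour-related symptom. The decision limits are tight: 3 of 12 to continue and 8 of 25 for a positive trial. A misattributed success moves the count in one direction only.

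**Working it through.** **Step 1. Follow an irradiated target lesion through the rules.** A participant has radiotherapy to a target lesion under Section 4 and stays on Minnelide. Nothing in 6.3.1 or 6.3.3.1 removes that lesion from the sum of diameters. Nothing in 6.3.3.3 closes best response at the date of radiotherapy; it closes at progression. If the lesion shrinks or stops growing because of the radiation, and nothing else meets PD, the sum yields PR or SD. Once confirmed, or once 16 weeks are reached, Section 10.1 counts disease control. If a new lesion appears or non-target disease clearly progresses, the result is PD whatever was irradiated.

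**Step 2. Reproduce the design (Section 10.3).** Inputs: p0 = 0.20, p1 = 0.40; stop if 2 or fewer of 12; positive if 8 or more of 25. With X ~ Bin(12, p) and Y ~ Bin(13, p):

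- Early stopping: P(X ≤ 2). At p = 0.20 this is 0.8^12 + 12(0.2)(0.8^11) + 66(0.2^2)(0.8^10) = 0.5583, the plan's 55.8%.
- Positive trial: sum over x = 3 to 12 of P(X = x) × P(Y ≥ 8 − x). This gives 0.0991 at p = 0.20 and 0.8151 at p = 0.40, consistent with alpha 0.10 and beta 0.20. A full search for the Simon optimal design returns the same 2/12 and 7/25.

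**Step 3. Effect of miscounted participants.** The documents give neither the frequency nor the effect of on-study radiotherapy, so this step is an assumption shown over a range. Let the true drug-only rate be 0.20, and let radiotherapy turn a fraction c of the remaining 0.80 into counted successes. The counted rate is q = 0.20 + 0.80c.

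| c | counted rate q | P(stop at stage 1) | P(positive trial) |
|---|---|---|---|
| 0 | 0.20 | 0.558 | 0.099 |
| 1.25% | 0.21 | 0.523 | 0.124 |
| 2.5% | 0.22 | 0.489 | 0.151 |
| 5% | 0.24 | 0.422 | 0.216 |
| 10% | 0.28 | 0.304 | 0.371 |

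One participant in 25 is 1/25 = 4 percentage points, the whole distance between 7/25 (28%, negative) and 8/25 (32%, positive).

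**Step 4. Price of counting irradiated participants as failures.** Such a rule can only lower the count, so the 0.099 error bound at a true 20% still holds. If a fraction g of truly controlled participants is irradiated early and lost, the counted rate under p1 is 0.40(1 − g). At g = 0, 5% and 10% this is 0.40, 0.38 and 0.36, and power is 0.815, 0.759 and 0.694.

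**The case against.** The strongest reply is that a false success is hard to obtain. The radiation must fall on a target that drives the sum. All other disease, uncontrolled by the drug, must also avoid PD long enough for a confirmed response or 16 weeks of stability. Radiotherapy after progression cannot help, because best response has closed and confirmed progression ends therapy (Section 3.9.1). This stands and limits how often the problem can occur. A reader might infer that any shrinkage or stability counts, or that radiation effects will necessarily be credited to the drug; the documents support neither. The endpoint has thresholds, and the radiotherapy is discretionary.

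It can also be said that the plan is merely silent. That is less persuasive. The sum, the best-response window and the endpoint definition are all stated, and applying them literally produces the count in Step 1.

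A reader might further infer that the plan breaches its own requirement in Section 6.3.1: "If the investigator thinks it appropriate to include them, the conditions under which such lesions should be considered must be defined in the protocol". That does not follow. The note concerns lesions in previously irradiated areas, so it bears on measurability at baseline and not on radiotherapy given on study. Most of the inclusion criteria in Section 2.1.1 are also absent from the text available, and a condition could stand there. The point here does not rest on that note.

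Finally, Section 4 requires concomitant medications and supportive therapy on the CRF, but does not name radiotherapy, its site or its date. A reader should not assume that these are already captured.

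**Conclusion.** The point holds in limited form. Applied as written, the plan can count a radiation effect on a target lesion as disease control in an endpoint meant to measure Minnelide alone. This can happen only when the irradiated target determines the classification. The error favours success only, and one participant can change either the stage 1 decision or the final one.

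Its size cannot be derived from the documents. The rise in false-positive probability from 9.9% to between 12.4% and 37.1% rests on an assumed true rate of 20% and assumed counted rates of 21% to 28%. The upper end requires radiotherapy to convert one in ten uncontrolled participants. It is an illustration of sensitivity and not a forecast. The sample size and decision rule are correct as stated.

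The counting rule should be fixed before the data are read, because a rule chosen afterwards could decide the result. Whether radiotherapy should be allowed is a clinical question and is not judged here.

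**What to change.** Leave the allowance in Section 4 unchanged and change only the counting, in Sections 6.3.3, 10.1 and 10.5.2:

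- Assessments of a target lesion after on-study radiotherapy to it do not support CR, PR or SD.
- A participant who has radiotherapy to a target lesion before a confirmed CR or PR, or before 16 weeks of SD, is documented counts as not having disease control in the primary analysis. The same rule applies at the stage 1 look.
- Radiotherapy to non-target sites does not change the count.
- Report the number of participants affected, with a sensitivity analysis that counts them by RECIST as observed.
- Confirm that the CRF captures the site and date of radiotherapy; add fields if it does not.

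The cost is protocol and SAP wording, and possibly two CRF fields. The sample size and the 3/12 and 8/25 limits stay as they are. The statistical downside is that a participant who truly benefits from the drug but is irradiated early counts as a failure. Power falls from 0.815 to 0.759 if this affects 5% of truly controlled participants, and to 0.694 at 10%. The sensitivity analysis shows how much the result depends on that choice.
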